WHTH Warrington and Halton Teaching Hospitals NHS Foundation Trust

Synopsis

Study Title	St andardisation of the Su p ine P elvic R a diograph T e chnique	
Short title	STOPPAGE	
Protocol version and	Version 1.	
date	23 rd March 2021	
Study design	Multi-centre interventional study	
Study participants	Patients referred for pelvic radiography	
Planned study sample	Retrospective audit across two NHS sites (Mid Yorkshire Hospitals Trust	
	(MYH) and Warrington and Halton Teaching Hospitals NHS Foundation Trust	
	(WHTH) of existing pelvic radiographs obtained in the same time period in	
	2019 (June to October).	
	Prospective convenience sample of patients attending either of the two NHS	
	hospitals for supine pelvic radiography. The target sample size is n=314	
	across two NHS sites. Recruitment will be on a 1:1 basis	
Planned study period	Recruitment July to October 2021.	
	Data analysis, write up and dissemination November 2021 to March 2022	
Primary objective	To standardise the acquisition of supine pelvic radiographs and determine	
	the reliability of a different evidence based centring point with respect to	
	sagittal axial and coronal rotation, image quality, and included anatomy.	
Secondary objectives	To assess if the different centring point reduces the number of repeat	
	radiographs required due to unacceptable technical quality	
	To determine the average radiation dose of the different centring point	
	compared with 'usual practice'	
	To determine the perceptions of locating bony landmarks for both	
	techniques amongst radiographers	
Underlying hypothesis	The different centring point will reduce variability in pelvic radiograph	
	measurements and be more acceptable to radiographers than the current	
	standard of positioning	

Summary

Radiographic projections should be standardised to enable consistent and accurate interpretation and measurements, but textbooks and clinical practice describe various methods.

This variation can lead to problems with measurements which determine patient outcomes, and this is particularly evident within pelvic radiography. This has implications for orthopaedic surgeons who need accurate measurements to plan hip replacements and assess the joints. In some instances, radiographers 'centre low' to demonstrate the hips, whereas others include iliac crests as a true 'pelvis'.

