The different centring point being evaluated at the interventional site is based on features of the key anatomy being studied (the hips) and could be relevant regardless of patient body habitus, anatomical variation (pelvic tilt) and orientation (supine or standing). There is a clear gap in knowledge as to whether centring derived from different surface anatomy reference points result in the same image, radiation dose, and diagnostic quality and there is a need for greater standardisation in clinical practice and a robust underpinning evidence base.

The aim of this study is to provide evidence for a different centring point that has been developed from a previous image review study [1, 33] and determine its reliability and acceptability to radiographers. Providing evidence for optimum position is the first step to ensure radiography is evidence based and allows future development of an evidence base for other body parts. In addition, it provides a platform from which to consider changes to technique, such as the increasing requirement for weight-bearing images.

Principal aim of the study

To validate a different centring point for pelvic radiographs in a supine position.

Primary research question

What is the variability between the different pelvic centring point in a range of patient body habitus?

Secondary research questions

- Does the different centring point undertaken at the interventional site lower the number of X-ray repeats when compared to usual practice undertaken at the control site?
- What is the variability in pelvic radiographs (i.e. rotation and inclusion of anatomy) with the different method versus 'usual practice'?
- What is the average radiation dose for the different centring point compared to usual practice?
- What are the perceptions of radiographers in the ease of using the different centring point?

Methods

This study will test the different centring point for reliability and acceptability. Two NHS clinical sites in England will be used with one undertaking pelvis radiography according to the different technique (intervention site) and the other continuing with standard practice (control site).

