Retrospective audit: Pelvic radiographs from both sites obtained for the same time period in 2019 (June to September) will be assessed for image quality and to identify any recurrent issues (rotation, included anatomy, and image quality). Differences and similarities between the two retrospective cohorts will be assessed. An update on the retrospective audit will be provided to both sites as part of the prospective study training (see below).

Prospective data collection: All radiographers at the interventional site will undertake training on the different centring point, consisting of a video presentation and online Q&A session to embed the different technique. The training will be based on the literature, retrospective audit, and the findings of a recent unpublished evaluation [24] and article in press [1], which demonstrated high variability of centring points within pelvic radiographs and supported the proposal for a different centring point.

The control group will have a refresher update on pelvic positioning based on the retrospective audit. They will then continue with their usual practice and the technique used to position the patient (identified anatomical landmarks; field centring) will be documented on a case report form.

Sampling strategy

Patients presenting for pelvic radiography who fit the inclusion exclusion criteria will be sent a participant information sheet (PIS) with their appointment or given one in clinic and/or on arrival in radiology. Posters explaining the research will also be placed in each Department's waiting area.

A core group of study delivery radiographers, who have received GCP research awareness training will be responsible for obtaining informed written consent at both sites. Patients who agree to take part will sign a consent form agreeing to participation. The number of patients approached versus the number recruited will be recorded in a screening log.

Sample size

Based on unpublished pilot data, we would aim to reduce centring point variation with an effect size of 75%. This would require a total sample size, between the two study sites, of 314 (significance level 5%, power 80%) and would be achievable given the workload between the sites. Recruitment would be on a 1:1 basis.

Eligibility

Patients presenting for pelvic radiography who fit the inclusion exclusion criteria presenting to either of the clinical sites for pelvic radiography within the study period

Inclusion criteria

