The research team will incorporate a rigorous programme of quality control. At regular intervals, study data will be exported from EDGE into an Excel spreadsheet and validated by a member of the research team with any data queries checked against source data. The main trial site (MYH) has an established monitoring audit programme for research studies with sponsored studies guaranteed to be appraised as part of this process, the same processes will be established at the other site (WHTH). Missing data will be recorded as an empty value.

Outcome measures

Statistical evaluation and data analysis

The data from the retrospective audit from both sites will be evaluated to determine the variability of axial, sagittal and coronal rotation; image quality, and included anatomy.

Prospective data from both sites will be analysed with descriptive and inferential statistics ICC's and Bland Altman plots (if the data is normally distributed). Data will be stratified according to Body Mass Index (BMI) in the following categories:

STOPPAGE protocol Version 1. 23.3.21 IRAS Project ID: 294098

- Underweight/Normal (BMI < 25)
- Overweight (BMI 26-30)
- Obese/morbidly obese (BMI >30)

Primary data analysis will determine the reliability of the centring point in the different technique versus usual care for sagittal, axial and coronal rotation; image quality, and included anatomy.

Secondary data analysis will compare results from within and between both sites to determine if the training and implementation of the different technique has any effect on the following:

- Obturator width left and right
- Axial pelvic rotation (degrees)
- Inter-acetabular line
- Pelvic outlet diameter
- Femoral head diameter left and right
- Inter-trochanter width
- Radiation dose
- Number of repeat radiographs
- Image quality as measured on the CRF form and from the exposure index
- Included anatomy from the iliac crests to the greater trochanters

For radiation dose data, and the number of repeats, the median and 75th percentiles will be compared.

The anonymised staff comments on the individual patient CRF's across both study arms will be descriptively analysed and a thematic analysis undertaken of any free text comments (see CRF Appendix 3).

Dose evaluation

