The data collected at both sites will include the radiation dose, measured as Dose Area Product (DAP). This will be compared to both local and national Diagnostic Reference Levels (DRL's) 2019 [34]. If any radiographs require repeating due to inadequate technical quality then these will be recorded along with the DAP. All repeat radiographs will be stored on PACS locally and transferred to the research team anonymously, no study images will be 'rejected'.

The radiographs will be undertaken with the use of Automatic Exposure Controls (AEC's) which feedback to the control panel and deliver the optimum radiation dose to the patient based on patient thickness and density (attenuation). Patient thickness will be calculated by subtracting the source object distance (SOD) from the source image distance (SID). Participant height and weight will also be recorded to allow evaluation of the effect of BMI on the subsequent radiographic technical quality.

The exposure Index (E.I.) will also be recorded for each patient. The E.I. is the measure of the amount of exposure received by the image receptor (IR). It is dependent on mAs, total detector area irradiated, and beam attenuation. The exposure index is indicative of the receptor dose, hence inherent signal to noise ratio (a measure of image quality)

Study Management

Patient and Public Involvement (PPI)

This proposal was developed with the advice and contribution of two Patient and Public Involvement (PPI) representatives from one of the study sites. The research idea was presented to the representatives and their views sought on the relevance of the research and appropriateness of the

research methods proposed. The PPI were consulted on, and approved all patient facing documents, and the group gave an opinion regarding privacy and dignity issues relating to obtaining patient size characteristics and the palpation of pelvic landmarks. Advice was incorporated and aided in a refined study proposal. PPI involvement will continue during study monitoring and when disseminating study findings. The PPI team will formally continue to the publishing of a lay summary of research findings.

Study Support

The CoRIPS grant is providing the funding. They will have no intellectual property (IP) rights to the data or outcomes arising from this study. Local CRN support will be sought help with recruitment and site file monitoring.

Dissemination

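### Comparing repeat radiographs by median and 75th percentile will very probably show 0 against 0 unless about a quarter of patients need a repeat; the named comparison does not serve the secondary objective

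*Protocol*

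**What the plan says.** The Synopsis lists this secondary objective: "To assess if the different centring point reduces the number of repeat" radiographs that poor technical quality makes necessary. The secondary research questions put it as a comparison of sites: "Does the different centring point undertaken at the interventional site lower the number of X-ray repeats when compared to usual practice".

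On data capture, the section on dose evaluation says: "If any radiographs require repeating due to inadequate technical quality then these will be recorded along with the DAP". Each patient therefore has a recorded count of repeats.

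On analysis, the section on statistical evaluation lists the number of repeats among the items to be compared within and between sites. It then gives one rule for dose and repeats together: "For radiation dose data, and the number of repeats, the median and 75th percentiles will be compared". No proportion, rate or test is named for repeats. A general sentence in the same section promises descriptive and inferential statistics for the prospective data, naming ICCs and Bland-Altman plots, and says the data will be stratified by BMI. No expected repeat rate appears anywhere in the Protocol.

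**The concern.** The median and 75th percentile suit a continuous, skewed quantity such as dose area product, and they allow comparison with diagnostic reference levels. A repeat count behaves differently. If most patients need no repeat, the middle of the distribution is zero, and so is its upper quartile. All the information lies in the minority above the 75th percentile, which neither statistic reaches.

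At stake is one of the study's secondary objectives. If the named comparison were the one reported, a real fall in repeat exposures would probably appear as identical zeros at both sites, and a real increase could be hidden in the same way.

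**Working it through.** **Inputs from the Protocol.** The total sample size is 314 at 5% significance and 80% power (section on sample size). On allocation: "Recruitment would be on a 1:1 basis". So n = 314 / 2 = 157 per site.

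**The Protocol's own figure.** The 314 was not derived for repeats. Its stated basis is: "we would aim to reduce centring point variation with an effect size of 75"%, with no outcome scale or SD, so it cannot be confirmed or refuted. Two-sided, a standardised mean difference of 0.75 needs 56 in total, an SD ratio of 0.75 needs 194, and a variance ratio of 0.75 needs 764. This point needs only about 157 per site, and the threshold below, as a percentage, hardly depends on n.

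**Step 1: when the quantiles leave zero.** Sort the 157 counts and use the linear-interpolation definition.
- The 75th percentile lies at position 0.75 × 156 + 1 = 118. It exceeds 0 only if at most 117 patients have no repeat, that is, if at least 157 − 117 = 40 have one (40/157 = 25.5%).
- The median is the 79th value. It exceeds 0 only if at least 79 patients have a repeat (79/157 = 50.3%).

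**Step 2: how likely that is.** Let p be the true proportion of patients with at least one repeat. The probability that a site's 75th percentile exceeds 0 is P(X ≥ 40) with X ~ Binomial(157, p). The rates are assumed, because the Protocol gives none.

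| p (assumed) | P(75th percentile > 0) |
|---|---|
| 5% | 1e-17 |
| 10% | 2e-8 |
| 15% | 0.0004 |
| 20% | 0.056 |
| 25% | 0.48 |
| 30% | 0.91 |

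For the median, P(X ≥ 79) is only 8e-8 even at 30%.

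**Step 3: a real effect that would not show.** Suppose the true rate is 20% at one site and 10% at the other. The probability that both 75th percentiles are 0 is (1 − 0.056) × (1 − 2e-8) = 0.944. The medians are then 0 as well. In the extreme, 39 of 157 patients with a repeat at one site and none of 157 at the other would still read 0 against 0, although Fisher's exact test gives p of about 2e-13.

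**Step 4: what a comparison of proportions could show.** This is the exact power of a two-sided 5% Fisher test at 157 per site, with assumed rates.

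| Rates | Power |
|---|---|
| 10% v 3% | 65% |
| 15% v 5% | 82% |
| 10% v 5% | 32% |
| 20% v 10% | 65% |

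The half-width of an approximate 95% CI for the risk difference is 1.96 × √[(p1(1−p1) + p2(1−p2))/157].
- 20% v 10%: 1.96 × √(0.25/157) = 0.078, so 10 ± 7.8 percentage points.
- 10% v 5%: 1.96 × √(0.1375/157) = 0.058, so 5 ± 5.8 percentage points.

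The second interval includes zero, but it shows the estimate and its uncertainty. Two zeros show neither.

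**The case against.** **The question is not closed.** A reader might infer that the repeats objective cannot be answered at all. The Protocol does not support that. Repeats are recorded whenever they occur, the general wording allows inferential statistics, and the percentile sentence does not say that it is the only comparison. An SAP that is not shown could add a proportion. This stands, and it limits the point to the comparison the Protocol names. It does not remove the point: for this outcome the Protocol is not silent but names a statistic that is probably uninformative, and a useful SAP analysis would have to go beyond it.

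**Repeats might be common.** The Protocol gives no rate, so a low rate is an assumption. At 30% the 75th percentile would usually exceed 0. Nothing in the Protocol suggests a rate that high, and immobile patients are excluded. Even then, quantiles of a small whole-number count would be a coarse comparison.

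**Site totals may be meant.** One total per site has no useful median or 75th percentile, so this reading does not help.

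**The alternative is not well powered.** This is true. A halving from 10% to 5% would be detected only about a third of the time. It is a reason to report an interval, not to keep a statistic that is expected to be zero.

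**Dose.** A reader might extend the criticism to dose, since exposure control responds to patient thickness and the site determines the technique. The Protocol does not support calling that an error: the same section stratifies the prospective data by BMI, and quantiles suit description against reference levels. It also gives no between-site difference in thickness from which a bias could be sized.

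**Conclusion.** The point holds for repeats only. If the true repeat rate is 15% or lower at both sites, the named comparison is practically certain to read 0 against 0. At 20% against 10% it does so with about 94% probability. Near 25% it is close to a coin toss whether a site's 75th percentile leaves zero. The named comparison therefore very probably cannot answer the secondary objective, although the recorded data can address it.

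The conclusion rests on three things: a repeat rate below about a quarter at each site (assumed), about 157 patients per site, and reading the number of repeats as a count per patient. It does not depend on whether 314 was derived correctly.

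Severity is should-fix. The outcome is secondary, the primary objective and data collection are unaffected, and the remedy uses data already planned. The dose comparison is not part of the defect.

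**What to change.** Split the sentence in the section on statistical evaluation in two.

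- **Dose:** keep the median and 75th percentile as description against the diagnostic reference levels. Adjusting for the sagittal diameter already collected is optional.
- **Repeats:** compare between sites the proportion of patients with at least one repeat for technical reasons, as a risk difference with a 95% CI and a Fisher test or logistic regression. Also report total repeats per 100 patients at each site.

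Add a sentence that the study was not sized for repeats and that precision is limited, with the Fisher powers above as illustration (82% for 15% v 5%, 32% for 10% v 5%), so that a non-significant result is not read as evidence of no difference.

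The cost is a wording change in the Protocol, carried into any SAP. No additional data, visits or patients are needed.
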